8.1. Summary of assessments

Figure 1 – Summary of assessments

	Pre- randomisation	Baseline (randomisation*)	Po	ost-rand	omisati	on
TIMEPOINT (days)	<day 0<="" th="">Day 0	t1	EoT (t+42)	60 **	120 Ω	</day>	Day 0	t1	EoT (t+42)	60 **	120 Ω
ENROLMENT:						
Eligibility screen	х					
Informed consent	х					
Care Home Randomisation		Х*				
INTERVENTIONS:						
IMP + standard care			•	-		
Standard Care			•			-
ASSESSMENTS:						
Demographics, medical history	х					
Outcome Events (care-home reported)			•		-	
Primary ordinal outcome components†					х	x
SAE/SAR/SUSAR			-	▶		
QoL (EQ-5D-5L, EQ-VAS)	х				х	
Resource use					Х	

t1: Day 1 of trial treatment, EoT: end of trial treatment, EQ-5D-5L: Euro-Quality of Life-5 dimension-5 level; EQ-VAS: Euro-Quality of Life-visual analogue scale; SAR: serious adverse reaction, SUSAR: Suspected unexpected S

 $^{\Omega}$ follow-up beyond 60 days to 120 days based on routinely collected health data only.

Trial	Prophylactic therapy in care homes trial	Protocol Final v1.) date:	13-May-2021	Page:	26 of 44
name:	U1111-1265-4068	version:				

^{*} For PrEP: care home will be randomised once an IMP has been identified by the NIHR POG and care homes are given the green light for randomisation. For PEP: care homes will be randomised once they have an indication of a developing infection e.g. recent positive PCR or lateral flow test (or equivalent) in a resident or member of staff (index case).

^{**} Primary ordinal outcome components and resource use cover the period from Day 0 to Day 60 and will be requested to complete data entry within 7 days of the day 60 timepoint by care home staff. Quality of life questionnaires will be completed at Day 60+/-2 and in accordance with the trial data management plan.

⁺ Primary (ordinal) outcome: no infection / infection (asymptomatic or symptomatic) but remains in home / admission to hospital allcauses / all-cause mortality. Ascertainment of the primary outcome measure will be performed centrally using UK death, hospitalisation and COVID-19 registers. Central and care home derived data will then be cross-checked.

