1.2.4. Timing of outcome measures

The key timings for each comparison are:

- End of treatment: 42 days
- Primary outcome based on routine national data: 60 days
- Clinical outcomes based on data from care homes: 60 days
- End of follow-up based on routine national data: 120 days
- End of trial: Once last resident has reached 120 days and data cleaned and analysed.

The explanation for separating the assessment of the primary outcome from end of treatment is that outcomes following acute COVID infection can be delayed. The median (IQR) time from symptom onset to death based upon ONS data is 14 (0-28) days.[6] Hence, assessing the primary outcome at 60 days following randomisation maximises the likelihood that we'll capture most adverse events associated with the infection, this based on a median outbreak duration of 28 days.

There is evidence that some older people with COVID deteriorate as a consequence of deconditioning and loss of physical function following acute infection. These adverse effects are related to physical deconditioning, rather than the direct effect of the virus, but they could be ameliorated by preventative therapies that reduce the likelihood, duration or severity of COVID infection. We have therefore included a 120 day follow-up point using routinely collected NHS data to gather information on how study treatments modify longer-term adverse outcomes as a consequence of COVID-19, e.g. long-COVID.

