8.2. Schedule of Assessments

Pre-Randomisation

- Eligibility screen
- Informed consent
- Demographics and medical history
- Quality of Life: EQ-5D-5L; EQ-VAS
- Number of residents in care home

For PEP only - At point of outbreak (care home level)

• Source of infection of SARS-CoV-2(resident, staff), date and type of test (lateral flow, PCR or equivalent).

Day 0 (randomisation)

• Number of residents in care home.

Days 1-EoT

- Administration of intervention if randomised to trial treatment (according to duration specified in IMP appendix).
- Safety: targeted adverse events and serious adverse events (including SARs)

Days 1–60

• Components of primary outcome.

Day 60(+/-2)

- QoL: EQ-5D-5L; EQ-VAS
- Healthcare resource use

Day 60 Care home level

- Number of residents in care home (whether in trial or not) who became SARS-CoV-2 positive
- Number of residents in care home.

Days 1-120 (based on routinely collected health data only after 60 days)

• Outcome: no infection; SARS-CoV-2 infection and stayed in care home; admission to hospital; died (most serious event experienced during the 120 days post-randomisation)

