Outcome measures	Description	Sourc	ces	Type of data	Analysis method
Participant receives dexamethasone in the care home for COVID-19	Use of dexamethasone in care home for COVID- 19	\checkmark	-	Time-to- event	Competing-risks survival regression with cluster– robust standard errors
Participant receives oxygen in the care home for COVID-19	Use of oxygen in care home for COVID-19 (for care homes with capacity to give oxygen)	\checkmark	-	Time-to- event	Competing-risks survival regression with cluster– robust standard errors
Time to SARS-CoV-2 infection* - positive PCR or lateral flow test (or equivalent) (i) with symptoms of COVID-19 (ii) without symptoms of COVID-19, (iii) Total, i.e., either with or without symptoms of COVID-19.	Time from randomisation to SARS-CoV-2 infection - positive PCR or lateral flow test (or equivalent). The date of the LFT test will be used as the date of event if LFT is positive and confirmed by the PCR test. (i) with symptoms of COVID-19 (ii) without symptoms of COVID-19 (iii) with/without symptoms of COVID-19	✓ (presence/ absence of symptoms)	✓ (PCR test results)	Time-to- event	Competing-risks survival regression with cluster– robust standard errors
Time to first admission to hospital [†]	Time from randomisation to first hospitalisation for any reason	\checkmark	~	Time-to- event	Competing-risks survival regression with cluster– robust standard errors
Cause specific hospital admission		\checkmark	~		Descriptive
Days alive and not in hospital †		-	✓	Continuous	Linear mixed-effect model
Time to death	Time from randomisation to death (all-cause) in days	\checkmark	✓	Time-to- event	Shared frailty model

PROTECT-CH (2033) Statistical Analysis Plan Final version 1.0 02-Aug-2021. Based on protocol version 1.0 Page 13 of 25

Written using WPD 16.5 version 3.0, 13-Sep-2018. Effective date: 13-Oct-2018. Template Author: [name]

Outcome measures	Description	Sourc	es	Type of data	Analysis method
Cause-specific mortality, including COVID-19, stroke, pulmonary embolism, myocardial infarction	COVID-19	~		Binary	Descriptive
	stroke			Binary	Descriptive
	pulmonary embolism		•	Binary	Descriptive
	myocardial infarction			Binary	Descriptive

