Electronic frailty index at 60 days	Electronic frailty index (eFI) The eFI is presented as a score (e.g. if 9 deficits are present out of a possible total of 36 the FI score = 0.25) - higher scores indicate increasing frailty. The eFI score is used to define frailty categories: - Fit (0 - 0.12) - Mild frailty (> 0.12 - 0.24) - Moderate frailty (> 0.24 - 0.36) - Severe frailty (> 0.36) A composite endpoint strategy will be used to handle the eFI outcome truncated due to death by adding an extra category for death to ensure that death equates to the worst outcome.	-	✓	Ordered categorical	Mixed-effect ordinal logistic regression
Ordinal outcome for the most serious event experienced during the 120 days post- randomisation	Four-level ordinal outcome: No SARS-CoV-2 infection, SARS-CoV-2 infection but resident remains in care home, Admission to hospital, all- cause and Death, all-cause.	✓	✓	Ordered categorical	Mixed-effect ordinal logistic regression
Clinical: care home level					

Page **14** of **25**

Written using WPD 16.5 version 3.0, 13-Sep-2018. Effective date: 13-Oct-2018. Template Author: [name]

Outcome measures	Description	Sourc	es	Type of data	Analysis method
Number of SARS-CoV-2 infections in residents in the care home	Aggregate infection rate in the care home. The numerator will be all confirmed SARS-CoV-2 infections including residents not participating in PROTECT-CH trial and the denominator will be the number of residents in the care home at randomisation.	✓	~	Rate (Proportion)	Linear regression (rate difference) and Poisson regression (rate ratio)
Additional Safety:					
Serious Adverse Reactions (SAR, excluding primary and secondary outcomes) and Suspected Unexpected SAR (SUSAR)		✓			
Adverse events relevant to the intervention as specified in relevant IMP specific appendix to protocol		✓			

*For PEP- only applicable for residents not positive at randomisation; [†]excludes residents with directive for no hospitalisation

Page **15** of **25**

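### The 120-day ordinal outcome loses its care-home source of infections at day 60; if registers are incomplete, its infected versus uninfected split may be biased, in a direction set by when infections fall in each arm

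*Protocol*

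**What the plan says.** Protocol 1.2.4 sets the windows: "Clinical outcomes based on data from care homes: 60 days" and "Primary outcome based on routine national data: 60 days", with routine national data continuing to day 120. A footnote to the assessment table in Protocol 8.1 gives "follow-up beyond 60 days to 120 days based on routinely collected health data only", and Protocol 8.2 repeats that the 120-day outcome is "based on routinely collected health data only after 60 days".

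The footnote to the assessment table in Protocol 8.1 adds that ascertainment of the ordinal outcome "will be performed centrally using UK death, hospitalisation and COVID-19 registers", followed by a cross-check against care-home data. Registers are therefore a source throughout. What ends at day 60 is the care-home contribution.

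Infection is defined by PCR or lateral flow test (Protocol 2.2). In SAP 2.4, Table 1, the 120-day row has ticks under both the eCRF and routine data, no mention of day 60, and a single mixed-effect ordinal logistic model. The only Table 1 row that describes the content of routine test data is time to infection, which names "PCR test results". Protocol 10.3 lists SARS-CoV-2 testing data among the linked sources without giving the test type.

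**The concern.** Level 2 of the 120-day scale is built from two sources in days 0-60 and one source in days 61-120. An infection that only the care home would have reported can enter the outcome early but not late. A late infection absent from the registers would not be a missing value. It would look like level 1, so the complete-case rule in SAP 4.5 would retain it as the best outcome. The sensitivity analyses in SAP 7.2 concern the primary outcome and do not vary the data source. SAP 7.5 changes the population, not the source.

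The loss rule is the same in both arms, but it cancels only if infections fall at similar times in both. Key timings put the end of treatment at 42 days, so the 120-day look comes about 11 weeks after treatment ((120 - 42)/7 = 11.1). If a drug delays infection past day 60, more of its infections fall in the less complete period, and the 120-day result could suggest lasting protection when infection was only deferred.

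**Working it through.** **The plan's own figures (Protocol 13.1).** The Whitehead formula is n per group = 6(z_a + z_b)² / [(ln OR)²(1 - Σp̄³)], with control proportions 60/15/10/15%, two-sided 5% and 90% power.
- OR 0.67 gives 541.8 and OR 2/3 gives 529.1, against the stated 530.
- Design effect: 1 + [(0.49² + 1) × 32 - 1] × 0.11 = 5.255, stated as 5.25.
- Homes: 2 × 530 × 5.25 / 32 = 173.9, stated as 174.

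Neither document gives a 120-day event distribution or a register capture rate, so the following inputs are assumptions.

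**Pure postponement (true OR 1.00).** By day 120 both arms truly have 47% at level 1, 20% at level 2, 13% at level 3 and 20% at level 4. Standard care has 15 points of level 2 by day 60 and 5 after. The drug moves a further d points past day 60. Capture is complete to day 60 and a share s afterwards. Admissions and deaths are fully captured throughout.

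Observed level 2 is 15 + 5s under standard care and (15 - d) + (5 + d)s on the drug. The difference is d(1 - s), and it is added to level 1 on the drug. Example with d = 8 and s = 0.4: standard care 15 + 2 = 17%, drug 7 + 5.2 = 12.2%, difference 8 × 0.6 = 4.8 points.

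The common OR comes from a proportional-odds model fitted to these proportions; values below 1 favour the drug. The standard error is SE(log OR) = √[12 × 5.25 / (6,400 × (1 - Σp̄³))], which is 0.106 to 0.108. The false-positive rate is the two-sided 5% rejection probability.

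| d | s | Level 2, standard care / drug | OR | False-positive rate |
|---|---|---|---|---|
| 5 | 1.0 | 20.0 / 20.0 | 1.000 | 5.0% |
| 5 | 0.9 | 19.5 / 19.0 | 0.989 | 5.1% |
| 5 | 0.8 | 19.0 / 18.0 | 0.977 | 5.5% |
| 5 | 0.6 | 18.0 / 16.0 | 0.954 | 7.2% |
| 5 | 0.4 | 17.0 / 14.0 | 0.931 | 10.1% |
| 8 | 0.9 | 19.5 / 18.7 | 0.982 | 5.3% |
| 8 | 0.8 | 19.0 / 17.4 | 0.964 | 6.4% |
| 8 | 0.6 | 18.0 / 14.8 | 0.928 | 10.8% |
| 8 | 0.4 | 17.0 / 12.2 | 0.892 | 18.5% |

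With registers only over all 120 days and a constant s, level 2 is 20s in both arms and the OR is 1.000 in every row.

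**Other timings,** built on the plan's 60-day control distribution:
- *Waning:* OR 0.67 to day 60, then equal late infection risk of 5% to 20%. True OR 0.687 to 0.723; observed 0.684 to 0.715 at s = 0.8 and 0.679 to 0.701 at s = 0.5. A small bias towards benefit.
- *Sustained effect,* true OR 0.670: observed 0.670 to 0.673. Essentially none.
- *Benefit only after day 60* (late risk 10% against 5%): true 0.921; observed 0.935 at s = 0.8 and 0.959 at s = 0.5. A bias towards the null.
- *No effect in either period:* 1.000.

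**The case against.** A reader might infer that late infections are in fact under-counted and that the 120-day odds ratio is therefore biased towards benefit. The documents do not support that, for four reasons.

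- **Capture is unknown.** The PCR label sits in a different Table 1 row. The 120-day row has no such restriction, Protocol 10.3 does not limit the test type, and the SAP's flow chart of test scenarios is not reproduced in the text available. That a lateral-flow-only infection counts on day 50 but not on day 70 is an inference.
- **Registers serve both periods.** They also cover admissions and deaths to day 120, so only the level 1 versus 2 split is exposed.
- **The direction is not fixed.** Late protection is plausible for antibodies, for which Protocol 1.2.2 mentions a wash-out of up to 6 months, and it reverses the sign.
- **The harmful case needs large delays.** Protocol 1.2 describes the agents then under consideration as post-exposure, and 1.2.4 gives a median outbreak of 28 days. Infections delayed only to days 43-60 still have both sources. Moving 5 or 8 of 15 early points past day 60 means 33% or 53% of them.

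It can also be said that Protocol 1.2.4 justifies the 120-day point by longer-term consequences such as long-COVID rather than by postponement, and that SAP section 7 treats secondary outcomes as supportive.

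All of this stands and limits the point. It does not remove it: the change of source is explicit, Table 1 does not show it, and no planned analysis would reveal its effect.

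**Conclusion.** The point holds as a conditional risk to one supportive secondary outcome. The change of source at day 60 is certain. A bias follows only if registers miss infections that care homes would have reported and the timing of infection differs between arms.

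Under the assumed postponement scenarios a true null would read as about 0.99 to 0.89. At 80% capture or better the odds ratio stays at 0.96 or above and the false-positive rate at 6.4% or below. The 18.5% figure is the worst cell of the table and should not be quoted as typical. These sizes rest on the assumed 120-day proportions, capture that is complete before day 60 and constant after it, and a design effect of 5.25 carried over from the 60-day outcome. The change is worth making because it is cheap, and because without it a 120-day finding of lasting benefit could not be told apart from an effect of the change of source.

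**What to change.** In SAP Table 1, state that eCRF data for the 120-day row end at day 60, and state whether the routine test data include lateral flow results. Analyse the 120-day ordinal outcome from routine data only over days 0-120, alongside the version that adds care-home reports to day 60. Base any claim of lasting benefit at 120 days on the two agreeing.

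The cost is one table row, one extra model run and no new data collection, since the routine data are already to be linked. The downside is that the register-only version drops early infections known only to care homes. Some residents may then be level 2 at 60 days and level 1 at 120 days, so the two scales are not strictly nested. The SAP should say so and report the number of such residents by arm, which would also indicate how much care-home reporting adds to the registers. The 60-day primary outcome needs no change.

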8.2. Schedule of Assessments

Pre-Randomisation

- Eligibility screen
- Informed consent
- Demographics and medical history
- Quality of Life: EQ-5D-5L; EQ-VAS
- Number of residents in care home

For PEP only - At point of outbreak (care home level)

• Source of infection of SARS-CoV-2(resident, staff), date and type of test (lateral flow, PCR or equivalent).

Day 0 (randomisation)

• Number of residents in care home.

Days 1-EoT

- Administration of intervention if randomised to trial treatment (according to duration specified in IMP appendix).
- Safety: targeted adverse events and serious adverse events (including SARs)

Days 1–60

• Components of primary outcome.

Day 60(+/-2)

- QoL: EQ-5D-5L; EQ-VAS
- Healthcare resource use

Day 60 Care home level

- Number of residents in care home (whether in trial or not) who became SARS-CoV-2 positive
- Number of residents in care home.

Days 1-120 (based on routinely collected health data only after 60 days)

• Outcome: no infection; SARS-CoV-2 infection and stayed in care home; admission to hospital; died (most serious event experienced during the 120 days post-randomisation)

8.3. Trial Procedures

Care home staff involved in the trial will be trained in the aspects of Good Clinical Practice relevant to their role in the trial and in trial-specific procedures including delivering trial assessments (e.g. EQ-5D, EQ-VAS), recording participant information, and assisting participants to take the IMP (where relevant).

Trial	Prophylactic therapy in care homes trial	Protocol	Final v1.0	date:	13-May-2021	Page:	27 of 44
name:	U1111-1265-4068	version:					

8.3.1. Sub studies

There are no planned sub-studies.

8.4. Discontinuation of trial intervention/trial status

At the discretion of the participant (or clinician/GP/personal legal representative), aspects of trial participation may be discontinued/adjusted for example:

- Discontinue IMP but continue follow-up in accordance with the trial schedule and continue to provide trial data and allow routinely collected health data to be obtained for use in the analysis.
- Discontinue IMP and trial data provision but allow routinely collected health data to be provided for inclusion in the trial analysis.
- Discontinue from participation in trial interview if optional consent was given (See section 12.4).
- Participants may also choose to withdraw (or be withdrawn by clinician or personal legal representative) from trial intervention and all subsequent data collection.[‡]

Participants will be withdrawn from treatment at the wishes of the resident or personal legal representative, or at the discretion of the care home manager, principal investigator, general practitioner or chief investigator if continuation in the trial is deemed to be against the participant's best interest.

Treatment will be stopped if:

• Participant is hospitalised for COVID-19. (Treatment may be restarted if the participant returns to the care home within the treatment period.)**

• Participant experiences unacceptable drug reaction as specified in the IMPD appendices. Participants who have been withdrawn from the trial treatment and are experiencing ongoing toxicity will be followed up until the adverse reaction concludes. In the event of a Participant being withdrawn from the trial treatment, they will continue to receive the most appropriate standard of care treatment available under the guidance of their general practitioner or other treating clinician.

‡NB data collected prior to withdrawal will not be deleted and will be included in analyses. Routinely collected health data will still be obtained for use in the analysis unless the participant (or personal legal representative) explicitly states otherwise.

**IMP should not be sent with the resident if they are admitted to hospital, i.e. the IMP should not be administered in hospital. If the resident returns to the care home before the end of the treatment period, then it should be restarted and continued up to the original planned stop date.

9. Adverse Event Reporting

It is expected that participants in the trial will have a range of underlying co-morbidities and so infection with SARS-CoV-2 may lead to serious and significantly life-threatening conditions, which are outcomes for this trial. Safety reporting in the trial will therefore focus only on those events that could be related to the trial medication, are serious in nature (according to the SAE definition below) and are unexpected (either the event itself or in severity) according to the reference safety information (RSI) for the IMP. Further information regarding the RSI can be found in the appendix for each IMP. Once an intervention has been identified by the NIHR Prophylaxis Oversight Group, the risk profile of the IMP will determine any further safety reporting requirements beyond those described below. These will be detailed within the IMP appendix.

Trial	Prophylactic therapy in care homes trial	Protocol	Final v1.0	date:	13-May-2021	Page:	28 of 44
name:	U1111-1265-4068	version:					

The known or anticipated side effects of the IMPs are listed in the IMP appendices. Side effects will be apparent to residents with capacity and to care home staff. In particular, care home staff know their residents and their medical problems intimately and so can see deterioration very early; indeed side effects are likely to be identified earlier and potentially more frequently than they would be in people living in their own home. We will train care home staff to look for side effects through training at the site initiation visit and in videos available for download via the trial website. If side effects are apparent, care home staff may inform the resident's GP. All side effects will be entered into the trial database on a weekly basis by care home staff. Serious adverse events, hospitalisation and death will all be reported in real time via the trial database for review by the relevant principal investigator, for independent review by the medical adjudicator and Data Monitoring Committee, and for forwarding to the competent authority within the standard reporting periods relevant to SAEs, SARs and SUSARs.

A serious adverse event that is not expected against the RSI and considered to be related or suspected to be related to the IMP is classed as a Suspected Unexpected Serious Adverse Reaction (SUSAR) and requires expedited reporting as per the clinical trials regulations.

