4.2. Analysis sets

Outcome	Analysis set
Primary, secondary and safety outcomes – individual-level	Contemporaneously randomised care homes and their eligible residents analysed according to the group their care home was randomly allocated to regardless of adherence to trial allocation (Intention-to-treat [ITT] analysis population).
	Since not all residents will be eligible for all trial interventions, residents in homes allocated to standard care will only be included in a given comparison if they were eligible to be given the intervention of interest had their home been randomised to it (i.e. not taking the intervention of interest, or another drug in the same class, and did not have any contraindications to it).
	In the case where an outbreak based on a positive result from a lateral flow test is not confirmed with a PCR test, then the site remains in the trial in the ITT analysis population.
	Primary analysis will be for participants with complete outcome data collected (i.e., without imputation for missing data).
Care home level infection rate	All residents in contemporaneously randomised care homes including residents not consenting to PROTECT-CH included in the comparison.

Outcome	Analysis set		
Supplementary analyses (for	All residents with consent regardless of whether		
primary outcome and the	eligible/took part in treatment phase of trial, analysed according to the group their care home was randomly allocated.		
secondary outcome related to			
transmission (time to SARS-			
CoV2 infection))			

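### Protocol 8.4 lets a clinician or GP end a resident's eCRF data collection along with treatment, so outcomes held only in the eCRF may go missing unequally between arms

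*Protocol*

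**What the plan says.** Protocol 8.4 opens with a shared discretion: "At the discretion of the participant (or clinician/GP/personal legal representative), aspects of trial participation may be discontinued/adjusted". Four options follow. The first stops drug and keeps everything else: "Discontinue IMP but continue follow-up in accordance with the trial schedule and continue to provide trial data". The second is "Discontinue IMP and trial data provision but allow routinely collected health data to be provided for inclusion in the trial analysis". The third concerns the optional interview. The fourth is "Participants may also choose to withdraw (or be withdrawn by clinician or personal legal representative) from trial intervention and all subsequent data collection".

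The next paragraph, on withdrawal in the resident's best interest, covers treatment alone: "Participants will be withdrawn from treatment at the wishes of the resident or personal legal representative, or at the discretion of the care home manager", and it goes on to name the principal investigator, GP and chief investigator. A footnote to the fourth option keeps data already collected and adds: "Routinely collected health data will still be obtained for use in the analysis unless the participant (or personal legal representative) explicitly states otherwise".

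Elsewhere, Protocol 6.3 leaves residents and care home staff unblinded, and Protocol 7.1 has the GP told which IMP the resident was allocated. SAP 4.2 analyses residents by their home's allocation "regardless of adherence to trial allocation", using participants with complete outcome data. SAP 4.5 plans no imputation, and the sensitivity analyses in SAP 7.2 include none for missing outcomes.

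**The concern.** A clinician may have good reason to stop a drug. That decision alone is not a reason to stop recording what happens next. Analysis by allocation regardless of adherence depends on outcomes being recorded after treatment ends.

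Both data-ending options are coupled to stopping IMP or trial intervention. In an open-label trial with a no-treatment comparator, one trigger for such a decision, a suspected reaction to the drug, can arise only in IMP homes. Professionals' use of these options may therefore differ by arm and be related to prognosis. If it does, the outcomes without a routine source would be compared between groups with unequal and informative missingness, and nothing in the plan would recover or test for it.

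**Working it through.** **1. Who can end what under 8.4**

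| Data stream | Resident or legal representative | Clinician | GP |
|---|---|---|---|
| IMP | yes | yes | yes |
| eCRF data, second option | yes | yes, by the lead-in | yes, by the lead-in |
| All later data, fourth option | yes | yes, named | not named |
| Routine data, footnote | yes, if stated explicitly | no | no |

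The second and third rows let professionals end data collection. The best-interest paragraph and the footnote take the opposite approach. The fourth option's wording also conflicts with its own footnote, since routine data continue after a withdrawal described as covering everything.

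**2. Which outcomes have no second source**

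SAP Table 1 shows no routine source for dexamethasone or oxygen use in the home, and takes symptom status from the eCRF. Targeted adverse events are entered by care home staff (Protocol 9.4.1, SAP 8.2). EQ-5D-5L is a day-60 questionnaire (Protocol 8.2). By contrast, Table 1 gives both sources for levels 2 to 4 of the primary outcome. The notes to Protocol Figure 1 and SAP 4.5 say the primary outcome is ascertained centrally from death, hospitalisation and COVID-19 registers.

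**3. The plan's own sample size**

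For the ordinal outcome, n per group = 6(1.960 + 1.282)² / [ln(OR)² × (1 − Σp̄³)]. With control proportions 60/15/10/15% this gives 542 at OR 0.67 and 529 at OR 2/3, against 530 stated. Design effect = 1 + [(0.49² + 1) × 32 − 1] × 0.11 = 5.255 (stated 5.25). Homes = 2 × 530 × 5.25 / 32 = 173.9 (stated 174). With 200 homes, power is about 93%. Complete loss of 10% of IMP residents would leave it at 92.8%. Sample size is not the issue.

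**4. Illustrative effect on the primary outcome**

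The rates are assumed: a share d of IMP residents lose eCRF data and none in standard care do. A proportional-odds model is fitted to the expected proportions with no true effect (60/15/10/15% in both arms). Three handling rules are compared:
- A: affected level 1 residents are dropped (level 1 multiplied by 1 − d, then rescaled).
- B: affected residents at levels 1 and 2 are dropped.
- C: all of their level 2 infections are missed and counted as no infection.

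| d | Residents (d × 3,200) | OR, rule A | OR, rule B | OR, rule C |
|---|---|---|---|---|
| 2% | 64 | 1.02 | 1.015 | 0.991 |
| 3% | 96 | 1.03 | 1.022 | 0.987 |
| 5% | 160 | 1.05 | 1.038 | 0.978 |
| 10% | 320 | 1.10 | 1.081 | 0.957 |

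If only a quarter of the infections under rule C are missed, the range is 0.998 (2%) to 0.989 (10%). With a true OR of 0.67 and d = 3%, rule A gives 0.69.

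For scale, the effective size per arm is 3,200 / 5.255 = 609. With no effect, 1 − Σp̄³ = 0.776, so SE of log OR ≈ √[6 / (609 × 0.776)] = 0.113. The 3% shift under rule A is ln(1.029) / 0.113 ≈ 0.25 SE, which would take a nominal 5% two-sided error to about 5.7%.

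**5. Outcomes held only in the eCRF**

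No such backstop exists here. For anyone withdrawn this way, the information is lost from the stopping date. The SAP does not say how these residents enter the time-to-event analyses. Censoring them at withdrawal would assume that withdrawal is unrelated to later risk.

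**The case against.** A reader might go further and infer any of four things that the documents do not support.

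- *Data will be lost from the IMP arm.* No withdrawal rates are given, and the permission covers both arms. Deterioration occurs in standard care too: the sample size assumes 10% admitted and 15% dead there. The first listed option keeps full follow-up. A difference between arms is a risk, not a certainty.
- *The primary analysis is defeated.* Only the resident or representative can stop routine data, and Protocol 1.2.4 bases the primary outcome on routine national data. Rule A depends on reading the dash against level 1 in SAP Table 1 as making that level eCRF-only, which conflicts with central register ascertainment. No rule says a linked resident without eCRF data is dropped. Under rule C the shift reverses.
- *Safety follow-up stops for those taken off drug.* Protocol 8.4 itself keeps following ongoing toxicity, 9.4.3 follows SARs to resolution, 9.3 requires SUSARs whatever the delay, and GPs may report SAEs (9.4.2). What is exposed is mainly non-serious targeted events.
- *Professionals have the resident's authority over every option.* The fourth option does not name the GP, and the footnote denies professionals control of routine data.

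It can also be argued that stopping data collection may be in a resident's interest: about 76% are expected to lack capacity, and a questionnaire can burden someone who is unwell. That has some force for EQ-5D-5L self-completion, but Protocol 13.3 already provides for proxy report, and staff entries ask nothing of the resident. SAP 5.1 reports discontinuations by arm with reasons. That would reveal unequal use but not restore the data.

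**Conclusion.** The point holds as a limited, avoidable weakness. Protocol 8.4 gives professionals who may know the allocation a stated permission to end eCRF collection without a request from the resident or representative, and its own best-interest paragraph and footnote are drawn more tightly. The exposure is confined to outcomes without a routine source: symptom status, dexamethasone and oxygen use in the home, non-serious targeted adverse events and EQ-5D-5L.

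The size cannot be derived from the documents. At an assumed 3% in the IMP arm, about 96 residents would have these outcomes incomplete. For the primary outcome, the illustrative shifts at 2–10% run from 0.957 to 1.10 around a true OR of 1. They are small at the lower rates, depend on the handling rule for their direction, and are avoided where registers determine the level. The change is worth making because data not recorded cannot be recovered and the change is cheap. It is not a threat to the trial's main conclusion.

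**What to change.** In Protocol 8.4:

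- State that a decision by a clinician, GP or other professional ends trial treatment only, and that scheduled eCRF and routine follow-up then continue by default unless the participant or personal legal representative asks for data collection to stop.
- Remove the clinician from the fourth option, and exclude clinician and GP discretion from the second.
- Reconcile the fourth option's reference to all later data with the footnote that keeps routine data.

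The withdrawal form should match. The cost is a few words, plus continued eCRF entries by care home staff for a few more residents, with proxy EQ-5D-5L where self-completion would be a burden. Residents and representatives keep full control of their data. The sample size and every rule on stopping treatment stay as they are.
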